# **Endpoints**

- Achieving a one point or greater decrease from baseline in NP Score at Week 52 without first having nasal surgery (actual) or disease-modulating medication for CRSwNP.
- Achieving a meaningful decrease from baseline in their mean individual symptoms VRS and composite VRS from Week 49 through to Week 52 without first having nasal surgery (actual) or disease-modulating medication for CRSwNP.
- Achieving an 8.9 point or greater decrease from baseline in SNOT-22 total score at Week 52 without first having nasal surgery (actual) or disease-modulating medication for CRSwNP.

## **Model Specification**

The conditional treatment effect for the responder analysis endpoints will be estimated using
a generalized linear mixed model with a logit link function and covariates of treatment group,
baseline score, log(e) baseline blood eosinophil count, region, previous surgery for nasal
polyps, visit and interaction terms for visit by baseline score and visit by treatment.

#### **Model Checking & Diagnostics**

 Pearson residuals will be plotted by using PLOTS=PEARSONPANEL option for the model statement in SAS.

#### **Model Results Presentation**

- For each scheduled visit / time-period the following will be presented:
  - The number and percentage of responders and non-responders for each treatment, together with the odds ratio, 95% CI and p-value will be presented for the NP responder endpoint, and nasal obstruction, loss of smell, and rhinorrhoea VRS responder endpoints only
  - Other individual symptom VRS and composite VRS responder endpoints (facial pain, mucous in throat, composite nasal polyps symptoms, composite CRS symptoms and facial pain) will be summarized only

# 4.5. Safety Analyses

The safety analyses will be based on the Safety Analysis Set, unless otherwise specified.

## 4.5.1. Extent of Exposure

Two doses of study treatment will be administered during study treatment period: the first at randomization Visit 2 (Week 0) and the second at Visit 10 (Week 26). Each dose is viewed as providing therapeutic coverage for 26 weeks (182 days). The number of treatments administered, and the number of days exposure will be summarized descriptively and listed. Total subject-year exposure will also be presented.

Number of days of exposure to study treatment will be calculated as follow:

Duration of Exposure in Days = (Date of Final Dose) – (Date of First Dose) + 182 days (regardless of study withdrawal or death)

Subject years exposure is calculated as follow:

Subject Years Exposure = ((Date of Final Dose) – (Date of First Dose) + 182)/365.25

#### 4.5.2. Adverse Events

Adverse events analyses including the analysis of adverse events (AEs), Serious AEs (SAEs) and other significant AEs will be based on GSK Core Data Standards. Adverse events will be coded using the standard Medical Dictionary for Regulatory Affairs (MedDRA dictionary). The details of the planned displays are provided in the Programming Specifications document.

For the standard AE tables, the number and percentage of participants with AEs will be summarized for each treatment group by system organ class (SOC) and preferred term (PT). The ordering of the SOCs and the PTs within the SOCs will both be in descending order of total incidence. A SOC will not be presented when the overall incidence for any AE within the particular system is zero. If the total incidence for any two or more AEs is equal, the events will be presented in alphabetical order.

An overview summary of AEs, including counts and percentages of participants with any AE, AEs related to study intervention, AEs leading to permanent discontinuation of study intervention or withdrawal from study, SAEs, SAEs related to study intervention, fatal SAEs, and fatal SAEs related to study intervention will be produced.

A study intervention-related AE is defined as an AE for which the investigator classifies the possible relationship to study intervention as "Yes". A worst-case scenario approach will be taken to handle missing relatedness data, i.e. the summary table will include events with the relationship to study intervention as 'Yes' or missing.

#### 4.5.2.1. Adverse Events of Special Interest

Adverse events of special interest (AESI) include:

Allergic reactions including anaphylaxis

Note: these events will be assessed by the investigator as to whether they meet the diagnostic criteria for anaphylaxis as outlined by the 2006 Joint National Institute of

Allergy and Infectious Disease (NIAID)/Food Allergy and Anaphylaxis Network (FAAN) Second Symposium on Anaphylaxis [Sampson, 2006].

- Type III hypersensitivity (immune complex disease/vasculitis) reactions
- Local injection site reactions
- QTc prolongation: AESI of QTc prolongation will be summarized as detailed in Section 4.5.3.3.

A summary table showing the number and percent of subjects with each type of AESI (excluding QTc prolongation) broken down by preferred term will be created. An additional table will also display the relative risk and risk difference and their 95% CIs between and depemokimab and placebo.

For each type of AESI (excluding QTc prolongation) a profile summary table will be produced containing information including, but not limited to, the number of occurrences of the event, event characteristics, time to onset, intensity, outcome and action taken.

## 4.5.3. Additional Safety Assessments

## 4.5.3.1. Laboratory Data

Summaries of laboratory data including chemistry and haematology parameters, and liver function test data will be based on GSK Core Data Standards and unless otherwise specified will include on-treatment and post-treatment data. Change from baseline values for clinical chemistry and haematology will be summarized in separate tables using descriptive statistics.

A scatter plot of maximum post-baseline ALT vs maximum post-baseline total bilirubin will be produced. In addition, if any liver stopping or liver monitoring events occur during the study, summaries of liver monitoring/stopping event reporting and hepatobiliary laboratory abnormalities will be produced.

#### 4.5.3.2. Vital Signs

Systolic blood pressure, diastolic blood pressure, pulse rate and body temperature including change from baseline will be summarized at all visits and listed.

#### 4.5.3.3. ECG

Change from baseline (for post-baseline timepoints) values for all ECG measurements and intervals will be summarized by visit. ECG results will also be listed.

Individual maximum QTc(F) values will also be summarized to show the number of subjects with maximum values (msec) that increased to the following categories:  $\leq$ 450, 450 < to  $\leq$ 480, 480< to  $\leq$ 500, 500< to  $\leq$ 530 and >530. QT uncorrected values will be summarized to show the number of subjects with maximum values in the following categories: <600 and  $\geq$ 600.

Additionally, individual maximum changes from baseline in QTc(F) values will be summarized to show the number of subjects with maximum changes (msec) in the categories:  $\leq 30$ , > 30 to  $\leq 60$  and > 60.

All ECG values for participants with protocol defined QT stopping criteria will be listed.

Additional analyses related to ECG will be presented in a separate analysis plan as part of the Integrated Summary of Safety.

#### 4.5.3.4. Immunogenicity Analysis

For the immunogenicity assessment, two types of anti-drug antibody (ADA) assays will be performed, a binding antibody assay and a neutralizing antibody assay (NAb).

For the binding assay, there will be a three-tiered analysis: screening, confirmation and titration. The screening assay produces a result of positive or negative relative to a screening cut point. Positive samples continue with the confirmation assay, which also produces a result of positive or negative relative to a confirmation cut point. For positive confirmation samples, a titer value will also be obtained to quantify the degree of binding in a titration assay, and the sample will be tested with the neutralizing assay, which also reports results as positive or negative. A sample that is positive in the confirmation assay is considered positive for anti-depemokimab antibodies.

All participants' baseline immunogenicity samples will be analyzed. Post-baseline immunogenicity samples will only be analyzed for participants receiving depemokimab 100 mg SC.

The following descriptive summaries will be presented for depemokimab 100 mg SC group by visit using the Safety Analysis Set:

- Summary of binding antibody assay results: it will summarize the binding antibody
  confirmatory assay results at each visit. Summary will include categories for
  negative and positive results, sub categories for transient positive and persistent
  positive (see note below), and available titer values (min, median and max). It will
  also summarize the highest post-baseline binding antibody confirmatory assay result
  obtained.
- Summary of binding antibody results for participants without positive result prior to dosing: it will summarize the binding antibody confirmatory assay results at each visit. Summary will include categories for negative and positive results, sub categories for transient positive and persistent positive (see note below), and available titer values (min, median and max). It will also summarize the highest post-baseline binding antibody confirmatory assay result obtained.
- Summary of neutralizing antibody assay results: it will summarize the neutralizing
  antibody assay results for participants with a positive binding antibody confirmatory
  assay results. Neutralizing antibody assay results will be categorized as positive or
  negative. It will also summarize the highest postbaseline neutralizing antibody assay
  result obtained.

- Summary of AE by highest post-baseline binding antibody confirmatory assay result The following descriptive summaries will be presented for the placebo group using FAS:
- Summary of binding antibody assay results for all baseline visit results. Summary will include categories for negative and positive results, and available titer value (min, median and max).
- Summary of neutralizing antibody assay results for all baseline visit results. Summary will include categories for negative and positive results.

Note: Visits will include pre-dose baseline visit and all post-baseline visits where immunogenicity assessments were performed. The binding antibody confirmatory assay results are categorized as negative or positive. The positive results will have two sub categories: transient positive (defined as a single confirmatory positive immunogenic response that does not occur at the final study assessment) or persistent positive (defined as a confirmatory positive immunogenic response for at least 2 consecutive assessments or a single result at the final study assessment). For the summary of highest post baseline binding antibody confirmatory assay result and neutralizing antibody assay result, subjects with both positive and negative results will be identified in the positive category. If a subject had titer results that fall into multiple titer result categories, they will be included in the highest category.

# 4.6. Clinical Pharmacology Data Analyses

# 4.6.1. Pharmacokinetic Analyses

Depemokimab plasma concentration samples are collected at discrete timepoints during the 52-week treatment period. Depemokimab plasma concentration will be summarized by visit (Depemokimab + SoC arm only) using the PK Analysis Set.

For the PK summaries, any premature discontinuation of study treatment will be handled using while on-treatment strategy where data will be included in the summary while a participant was on-treatment. Other intercurrent events such as NP surgery, all changes in background medication or start of a prohibited medication, COVID-19 related events and courses of systemic CS to be handled under the treatment policy strategy.

The PK data from this study will be included in a meta-analysis of the PK and PKPD data across all depemokimab studies available at the time of the analysis. Details of meta-analysis will be in a separate CPMS analysis plan.

# 4.6.2. Pharmacodynamic (PD) Analyses - Blood Eosinophils

Blood eosinophil counts will be loge-transformed. Non-detectable blood eosinophil values of 0 GI/L, or results below the limit of quantification will be imputed with a value of 0.005 GI/L prior to log transformation. PD analyses will be analyzed using FAS.

Ratio to baseline during W52 will be analyzed using a MMRM analysis. Model specification, model checking, and diagnostics are the same as described for co-primary endpoints statistical analyses, see Section 4.2.2. Analysis will include data from all visits

that blood eosinophils data is collected. The LS Geometric Mean (SE Logs) blood eosinophil, the LS Geometric Mean ratio to baseline (SE Logs) blood eosinophil in each treatment group and the treatment ratio of LS Geometric Mean ratio to baseline (95% CI) for depending versus placebo will be presented in a table. The LS Geometric Mean and 95% CI of ratio to baseline blood eosinophil will also be presented graphically.

Absolute and ratio to baseline blood eosinophil counts will be summarized by treatment group and visit. Only results from the central laboratory will be included in the summary, however all data will be listed.

For the PD endpoint, the intercurrent event of initiation of a disease-modulating medication for CRSwNP will be handled under the hypothetical strategy, where PD data will be set to missing after the intercurrent event happened. Any premature discontinuation of study treatment will be handled using while on-treatment strategy where data will be included in the summary while a participant was on-treatment. Other intercurrent events such as NP surgery, all other changes in background medication or start of a prohibited medication (other than disease-modulating medications for CRSwNP), COVID-19 related events and courses of systemic CS to be handled under the treatment policy strategy.

The PK and eosinophils data from this study will be included in a meta-analysis of the PKPD data across all depemokimab studies available at the time of the analysis. Details of meta-analysis will be in a separate CPMS analysis plan.

# 4.7. IL-5 Analyses

The IL-5 data from this study will be analyzed in the future and is not planned for reporting of the CSR.

# 4.8. Analyses to Support Regional Submission

Since the study will be used to support China and Japan regulatory submissions, a subset of study population, safety and efficacy analyses will be repeated using Safety-China and Safety-Japan analysis sets for safety analyses and FAS-China and FAS-Japan for study population and efficacy analyses. The Programming Specifications document will provide further details.

The China and Japan subpopulation analyses will employ the same model as the overall population analyses. For MMRM analyses, if the model cannot converge from what was originally defined (including repeated visits and covariates in the model), those will be adjusted to ensure model convergence and obtain stable estimations. Alternatively, no analyses will be performed, and only descriptive summaries will be produced.

# 4.9. Risk Benefit Analysis

A forest plot will be produced to display efficacy and safety data from analyses in adjacent panels using FAS and Safety Analysis Set respectively. The efficacy results will include co-primary endpoints. The efficacy results will be obtained from analyses described in Section 4.2. The AE results will be obtained from the analyses as described in Section 4.5.2.1 for the following categories of AEs:

- On treatment SAE
- Systemic reactions
  - o Allergic (Type 1 hypersensitivity reactions)
    - Anaphylaxis

Other systemic reactions

- Type III hypersensitivity/vasculitis
- Local injection site reactions

# 4.10. Other Analyses

# 4.10.1. Subgroup analyses

This section details the subgroups of interest within this study.

Table 1 Subgroups of Interest

Subgroup	Category
Age 1	12-17, 18-64, 🛮 65
Age 2	12-17, 18-64, 65-74, 🛮 75
Age 3	18-39, 40-64, 🛮 65
Sex	Male, Female
Race 1	American Indian or Alaska Native, Asian, Black or African American, Native Hawaiian or Other Pacific Islander, White
Region 1	Europe (Belgium; Germany; United Kingdom; France; Netherlands; Spain), United States (US), Rest of the World (RoW) (Canada; Argentina; China; Japan)
Region 2	Asia, Non-Asia
Number of Previous NP Surgeries	0, 1, 2, >2
Baseline Eosinophil Category	<0.30 GI/L, >=0.30 GI/L
Participant with Asthma	Yes, No

Subgroup analyses should be interpreted with caution, especially when low numbers are observed in subgroups. If any subgroup category contains <20 participants, then the subgroup categories may be refined, if appropriate. Alternatively, no analyses will be performed, and only descriptive summaries will be produced for the subgroup.

## 4.10.1.1. Co-Primary and Pharmacodynamic Endpoint Subgroup Analyses

Subgroup analyses will be performed for the co-primary endpoints and the pharmacodynamic endpoint:

- Change from baseline in total endoscopic NP score at Week 52 (centrally read)
- Change from baseline in mean nasal obstruction score (verbal response scale [VRS]) from Week 49 through to Week 52
- Ratio to baseline in absolute blood eosinophil count at measured timepoints during the 52-week period.

The subgroup analyses will be conducted by the following subgroups: Age 3, Sex, Region 1, Number of Previous NP Surgeries, Baseline Eosinophil Category, and Participant with Asthma.

The subgroup analyses will be analyzed in the same way as the co-primary endpoint analyses described in Section 4.2.2; however, it will be adjusted for additional covariates. The additional covariate terms include: subgroup, subgroup by treatment, and subgroup by visit by treatment. The subgroup by treatment interaction term will be tested at the 10% significance level. When a subgroup assesses the same or a similar parameter as one of the covariates already in the model (e.g. region subgroup similar to baseline region covariate), the covariate will be removed from the model.

In the event the subgroup analysis model fails to converge, model simplification methods may be addressed (i.e. adjusting covariate structure, streamlining time points, combining subgroups, running model separately for each subgroup level).

The following will be presented for each endpoint:

- For each visit / time-period, the adjusted mean change from baseline (or ratio to baseline where applicable) with corresponding standard error for each treatment group will be presented. The estimated treatment difference will be presented together with 95% CI for the difference.
- For the end-of-study (EOS) visit / time-period only, a forest plot will be produced to present estimated treatment differences and 95% CIs including all subgroups. The subgroup by treatment interaction p-value will also be presented.

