# 4.2. Primary Endpoints Analyses

#### 4.2.1. Definition of endpoints

The co-primary endpoints are:

- a) Change from baseline in total endoscopic NP score at Week 52 (centrally read)
- b) Change from baseline in mean nasal obstruction score (verbal response scale [VRS]) from Week 49 through to Week 52

The total endoscopic NP score is assessed in the clinic at visits 2, 5, 7, 9, 11, 13, 15 and 16, or early withdrawal visit (weeks 0, 12, 20, 26, 32, 40, 48 and 52). The score is then graded by independent reviewers at a central lab who are blinded to treatment. The total score is reported as the sum of the right and left nostril scores and ranges from 0 to 8, with higher scores indicating greater disease severity. Non-missing scores must be available for both sides for the combined score to be calculated; otherwise the score will be set to a value of 9 to indicate a missing or unreadable value.

The nasal obstruction VRS score will be collected daily in the morning via the eDiary. Each day the participant will indicate the severity of their symptoms giving a score ranging from 0 to 3, with the 4 options indicating no symptoms, mild symptoms, moderate symptoms, and severe symptoms. The daily data will be collapsed into thirteen 4-week time periods, with the value for each time period based on the average of the non-missing days covered by that time period as described in Section 6.3.4.2. For each 4-week time period the average will only be derived if there are non-missing values for at least 4 days out of 7 in at least 3 out of 4 weeks, with at least 15 minimum values, otherwise it will be set to missing.

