#### **Model Checking & Diagnostics**

 The Kenward-Roger (KR) method [Kenward, 1997] for approximating the denominator degrees of freedom and correcting for bias in the estimated variance-covariance of the fixed

- effects will be used in the analyses. This will be achieved by specifying the DDFM=KR option in the MODEL statement within PROC MIXED.
- For mixed model repeated measures (MMRM) models, an unstructured covariance structure for the R matrix will be used by specifying 'TYPE=UN' in the REPEATED statement.
  - In the event that the model fails to converge, model simplification methods will be considered (e.g., adjusting covariate structure, streamlining timepoints)
- Appropriate graphs will be reviewed as part of the model checking process to ensure that
  distributional assumptions hold. These will include a normal probability plot of the residuals
  and a plot of the residuals versus the fitted values (checking the normality assumption and
  constant variance assumption of the model, respectively).

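### The subgroup interaction p-value shown with the end-of-study forest plot is not tied to the end-of-study contrast; read as the default PROC MIXED test, it averages over all visits

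*SAP*

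**What the plan says.** SAP 4.10.1.1 applies the co-primary MMRM of Section 4.2.2 to each subgroup factor and extends it: "The additional covariate terms include: subgroup, subgroup by treatment, and subgroup by visit by treatment". It then states: "The subgroup by treatment interaction term will be tested at the 10% significance level".

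Two kinds of result follow. The first is a set of treatment differences with 95% CIs at every visit or period. The second is a single-timepoint display: "For the end-of-study (EOS) visit / time-period only, a forest plot will be produced to present estimated treatment differences", and within the same bullet, "The subgroup by treatment interaction p-value will also be presented". No visit, contrast or test type is attached to that p-value.

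On software, Section 4.2.2 gives PROC MIXED with an unstructured covariance and Kenward-Roger degrees of freedom ("This will be achieved by specifying the DDFM=KR option in the MODEL statement within PROC MIXED"). Section 4.2.1 fixes the repeated measures. NP score is taken at the scheduled visits or the "early withdrawal visit (weeks 0, 12, 20, 26, 32, 40, 48 and 52"), which is 7 post-baseline visits. For the VRS, "The daily data will be collapsed into thirteen 4-week time periods". The co-primary endpoints themselves are at Week 52 and Weeks 49–52.

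**The concern.** The term named for testing is the two-way term. It is listed separately from the three-way term that lets subgroup differences vary by visit. In a model with both, the usual test of the two-way term concerns the subgroup difference in treatment effect averaged over visits. The plot shows that difference at end of study only. The two agree only if heterogeneity is constant over time.

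A reader will take the p-value as a test of the differences on the plot, and it can mislead in both directions. Heterogeneity that grows or appears late is diluted by the earlier visits. Heterogeneity that is real early but absent by Week 52 can give a small p-value beside end-of-study effects that show none.

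**Working it through.** **Inputs from SAP Section 5.** 118 evaluable participants per arm; SD 1.665 (NP score) and 0.84 (VRS); design differences 1.10 and 0.70. The SAP gives no power for the interaction test.

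**Assumptions not in the documents.** Subgroup split, correlation, size and time pattern of heterogeneity, and an SD that is the same at every visit. Power is two-sided at 10%, by normal approximation.

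**Step 1: the plan's own figures.** Smallest significant difference = 1.96 × SD × √(2/118). This gives 0.425 for NP score and 0.214 for VRS, against the stated 0.42 and 0.21. Power is 99.91% and above 99.99%, against the stated >99%. The inputs are therefore read correctly.

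**Step 2: what the two-way term tests.** The Type 3 hypothesis for subgroup by treatment was built numerically for the SAP's term list, with unequal subgroups and dropout. Covariates that are constant over visits were left out because they do not affect the visit weights. Every visit received equal weight: 1/7 = 0.143 for NP score and 1/13 = 0.077 for VRS. A three-level subgroup (2 df) gave the same NP weights. These weights depend on no assumed effect size or correlation.

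**Step 3: standard errors, two equal subgroups (59 per cell, four cells).**
- End-of-study contrast: SD × √(4/59) = 0.434 (NP), 0.219 (VRS).
- Visit average, compound symmetry: multiply by √[(1 + (m − 1)ρ)/m], where m is the number of visits or periods. NP: 0.328 (ρ = 0.5), 0.374 (ρ = 0.7). VRS: 0.160, 0.186.

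**Step 4: share of the full difference that survives averaging.**
- NP, linear growth from zero at Week 0: (12 + 20 + 26 + 32 + 40 + 48 + 52)/(7 × 52) = 230/364 = 0.632.
- NP, after Week 26 only: 4/7 = 0.571.
- NP, up to Week 26 only: 3/7 = 0.429.
- VRS, linear growth: 7/13 = 0.538.

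**Step 5: power at the 10% level.** NP difference between subgroups 1.0, VRS 0.5; ranges run over ρ = 0.7 to 0.5.

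| Pattern | End-of-study contrast | Visit-averaged term |
|---|---|---|
| NP, linear growth | 0.75 | 0.52–0.61 |
| NP, after Week 26 only | 0.75 | 0.45–0.54 |
| NP, constant | 0.75 | 0.85–0.92 |
| NP, up to Week 26 only (zero at Week 52) | 0.10 | 0.31–0.37 |
| VRS, linear growth | 0.74 | 0.42–0.51 |
| VRS, constant | 0.74 | 0.85–0.93 |

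**Step 6: sensitivity, NP score.**
- Correlation decaying at 0.80 to 0.95 per 4 weeks: the averaged term has 0.48–0.66 (linear), 0.42–0.58 (late), 0.81–0.95 (constant).
- Difference halved to 0.5: 0.31 for the contrast, against 0.22–0.25 (linear), 0.20–0.23 (late), 0.38–0.45 (constant).
- Three equal levels with effects −0.5, 0, +0.5 (2 df): 0.50 for the contrast, against 0.32–0.39 (linear), 0.28–0.34 (late), 0.61–0.72 (constant).
- SD rising linearly to 1.665 at Week 52 from 1.2 or 1.4 at Week 12, linear growth: the averaged term has 0.62–0.72 or 0.57–0.67.

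**The case against.** The p-value sentence sits inside the bullet that opens by restricting itself to end of study, so an end-of-study test may be what was meant. The SAP never names a Type 3 test. This reading is possible, but it conflicts with the earlier sentence that the model term is tested, and no end-of-study contrast is given. A programmer requesting the test of that term would not get the end-of-study one. Even on the favourable reading, the intent needs to be written down.

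If averaging was intended, it is defensible: it is the more powerful test under constant heterogeneity, nothing in the documents predicts a time pattern, and mid-study outcomes are themselves secondary endpoints. That stands as an argument for keeping the averaged test. It does not justify printing it unlabelled beside an end-of-study plot.

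The power figures lean on assumptions. A difference of 1.0 is 91% of the NP design effect (1.0/1.10), and at 0.5 both tests are weak. The constant SD may also fail. Worst scores assigned after surgery or a disease-modulating medication accumulate, which could raise variance towards Week 52; the rising-SD calculation shrinks the linear-growth loss and raises the cost of switching under constant heterogeneity. Both points stand and limit the size of the finding. Neither touches the visit weights.

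Misreading is partly guarded against: per-visit estimates are reported, Section 4.10.1 says "Subgroup analyses should be interpreted with caution, especially when low numbers are observed in subgroups", and no SAP rule acts on the interaction p-value. This limits the stakes.

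**Conclusion.** The concern holds. The SAP tests a term that is not tied to end of study and shows its p-value with an end-of-study plot. That the test is visit-averaged is an inference from the named term and the software default. On that reading, Week 52 carries 14.3% of the NP hypothesis and Weeks 49–52 carry 7.7% of the VRS hypothesis.

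The practical size depends on the unknown time pattern. Under the illustrative assumptions for NP score, the averaged term loses about 0.13 to 0.29 in power when heterogeneity grows or appears late, gains 0.10 to 0.17 when it is constant, and flags early-only heterogeneity about three to four times as often as the nominal 10%. Confidence in these figures is medium. Subgroup tests lie outside the multiplicity strategy and no primary conclusion is affected. The change should be made because it is cheap and makes the p-value answer the question the plot poses.

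**What to change.** In SAP 4.10.1.1, for the two co-primary endpoints, state that the forest-plot interaction p-value is the subgroup-by-treatment contrast at Week 52 (NP score) or Weeks 49–52 (VRS) from the same model, that is, the difference between subgroups in the end-of-study treatment effect. Use a multi-df contrast for factors with more than two levels: Age 3, Region 1 and number of previous NP surgeries. The visit-averaged test may be kept as an additional result if labelled as such. For the eosinophil endpoint, which is defined at timepoints across the 52 weeks, the averaged test can stay with that label.

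The cost is one sentence and one contrast statement per co-primary subgroup model, with no new data or model. The downside is lower power if heterogeneity is in fact constant over time: 0.75 against 0.85–0.92 for NP score and 0.74 against 0.85–0.93 for VRS, under the assumptions above.
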